### **3.8 Potential Limitations and Alternative Strategies**

We acknowledge there may be potential limitations to our approach. First, by only including non-surgical CR eligible patients we are limiting the generalizability of our findings to the non-surgical population studied. However, we recognize that the number of non-surgical eligible CR patients is significantly greater than the number of surgical patients typically enrolled in CR and that surgical patients (e.g. CABG) already have higher rates of CR participation. Counterintuitively, this has a potential benefit in that it opens additional lines for future research examining the predictors of referral, enrollment, participation, and completion of CR programs among surgical vs. non-surgical patients. Secondly, there is sparse data available on the ability of mHealth to improve patient-centered outcomes such as mortality. While we will plan to follow our enrolled participants for one-year in an effort to examine the impact of mHealth on this important patient-centric outcome, we recognize that the number of patients who suffer fatal cardiac or non-cardiac events will likely be relatively small. In an attempt to collect meaningful patient-centric data, our primary outcome for Aim 3 will be rehospitalization over this same time period. *[[Lastly, although the population of patients of African descent has increased substantially over the past few years in our community, we recognize the relatively homogeneous nature of the predominately Caucasian Olmstead County population. We have engaged directly with the Center for Health Equity and Community Engagement Research within the Office of Health Disparities Research to develop dedicated strategies to maximize our recruitment of minority populations and overcome this potential limitation to ensure appropriate representation. We have also added a co-Investigator with extensive experience working with African American research participants. Moreover, we have engaged with University of Minnesota Medical Center (Minneapolis/St. Paul urban area) to assist with additional recruitment of African American patients as needed. By partnering with this additional site, we will increase the pool of eligible minority patients located outside the confines of Olmsted County. Further, we will employ a multidimensional dynamic minimization algorithm to minimize imbalances between groups and ensure that the distribution of both women and minorities are appropriately distributed across all cohort arms of the study.]]*

### **3.9 Adverse Events (AE)**

Patients with (CAD) face negative effects of their conditions and/or surgical procedures which causes frequent Emergency Room (ER) visitation for conditions not related to the study. To better record any adverse events (AE) of this specific study, any AE notification will be notified to study PI. Which will deem its study relation by reviewing all EPIC ER documentations. Any AE will be reported to IRB and recorded in intelliTrial if the PI deems study related. In case of no study relation, a note will be put in subject folder for documentation purposes and will not be reported in intelliTrial.

[REDACTED]

[REDACTED]

[REDACTED]

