### 3) *Home-based CR + mHealth (HOM+):*

Participants will be provided paper copies of educational content at the time of event/discharge.

These participants will be provided access to the mHealth platform (as noted above). The mHealth platform provides “e-Learning modules” with factsheets, videos, quizzes, and questionnaires (coinciding with activities being conducted during the CON program), a Social Network Module will allow patients to communicate via secure network with other patients who are part of their invited network. The Social Network Module also allows for secure two-way interaction with healthcare providers if patients are experiencing signs or symptoms suggestive of worsening condition.

Participants will be given a blood pressure cuff and scale with which they are asked to measure their blood pressure and weight. The device setup will be performed onsite or at home (via video visit after shipping devices to the participant’s address). This data will be uploaded to the mHealth Personal Health Record Module. This module allows patients to upload, archive, and retrieve personal health data (e.g. fitness tracker data, heart rate monitor data, blood pressure recordings, etc.) and record vital signs, symptoms, treatments, and medical history.

Participants in this HOM+ group will be encouraged to exercise three days per week while also completing the additional questionnaires and educational content provided by the mHealth platform in accordance with the CR program. Participation will be tracked using web/internet analytics. Subjects in this arm of the study will have a remote visit (either video or telephone visit) with Cardiac Rehab staff once a week for 12 weeks.

Due to recent CMS changes, Home-based CR for patients randomized to the HOM+ group will be paid for by the study.

This three arm trial will allow us to make comparisons between a hybrid program of center-based CR which incorporates mHealth remote case management technology (CON+) to a traditional center-based program

alone (CON) as well as comparisons between home-based mHealth remote case management alone (HOM+) to a traditional center-based program (CON).

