### **3.4 Participant Recruitment**

*[[Male and Female patients, aged 18-80 years, who are identified as eligible for conventional CR will be recruited from the Mayo Clinic Health System (MCHS) (or our subcontract site University of Minnesota Medical Center [M Physicians/Fairview Health System]) by clinical research coordinators, referring physicians, and/or CR staff. We will make every attempt to recruit equal numbers of both men and women and appropriate distribution of minority participants.]]*

Inclusion Criteria: Patients must own, or have reliable access to, a smartphone or desktop computer with internet access, and an e-mail address. Eligible patients will have a history of one of the following: acute myocardial infarction/acute coronary syndrome, stable angina pectoris, percutaneous coronary intervention, or heart failure. Additionally, patients who underwent a surgical procedure which includes an indication for cardiac rehabilitation (coronary artery bypass surgery, heart valve repair/replacement, or heart transplant) will be enrolled but will only complete 6-minute walk test for measurement of exercise capacity per clinical practice guidelines.

Exclusion Criteria: Patients referred to CR with ventricular assist devices are not eligible. Patients who do not own, or have access to, a smartphone or desktop computer with internet access will not be recruited. Patient unable/unwilling to provide informed consent will not be enrolled.

The annual population of eligible CR patients at Mayo Clinic varies by diagnosis. As highlighted by Ades and colleagues report an annual nation-wide incidence of ~1,963,000 myocardial infarction, percutaneous coronary intervention, and systolic heart failure patients eligible for CR compared to only 395,000 coronary artery bypass surgery patients. While this list is clearly not inclusive of all eligible referral diagnoses, it provides an illustration of the disproportionate number of surgical vs. non-surgical patients eligible for CR. Importantly, despite the significantly larger number of non-surgical patients eligible for CR, it has been reported that CABG patients demonstrate higher rates of participation in CR^43.

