*[[Mayo Clinic has developed an in-house referral protocol for all patients meeting CR eligibility guidelines. Specifically, all patients visiting the clinic and/or hospital for one of the above inclusion criteria can be identified by our research team through the medical records, screened for eligibility, and approached to determine interest/willingness to participate in the study. This approach will maximize our potential to identify eligible individuals for screening and all patients who meet all eligibility criteria will be asked to participate. In 2018, the Rochester, MN CR program provided services for 459 new patients. Of those patients 68 were self-identified minority race or ethnicity (~15%) and 157 were women (~34%). Moreover, 365 patients were referred for non-surgical indications (~80%) which would meet the inclusion criteria of this proposal. Additionally, we have enlisted the assistance of an additional site in the Minneapolis/St. Paul metropolitan area (Hennepin County). The University of Minnesota Medical Center (M Physicians/Fairview) health network has 10 cardiac rehabilitation locations which provide cardiac rehabilitation services to ~4,000 new patients annually. Of these patients, ~3,000 receive their services within the Minneapolis/St. Paul urban area, many of which are from diverse racial and ethnic backgrounds.]]* We will maximize our retention by providing participants with remuneration for their time in the research program. This will include \$50 for the baseline visit, \$50 for the first follow-up visit at the end of the intervention, and \$50 for the final follow-up visit at 1-year post event. Payments will be made at the time the participant completes the final follow-up visit or informs a study team member of their desire to withdraw from the study.

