The social network module provides patients the ability to communicate, within a secure network, with their healthcare professionals (CR staff or research staff) who are part of their network. The network only includes patients and healthcare professionals involved in the CR program as part of the platform. Patients and care givers can have direct interactions through a chat function. Patient-caregiver (CR staff or research staff) interactions will only occur during regular outpatient clinical hours. This allows patients to ask questions, provide feedback, and communicate any possible issues that may arise. This also allows the CR staff and/or research staff to provide feedback, answer questions, provide clarification, and make changes to the individualized treatment plan (as would occur during conventional center-based CR during face-to-face conversations and interactions). Should an event or symptoms arise, patients will be instructed to go to their local emergency room and/or call 911 for assistance. The process for seeking medical attention is the same for all patients outside the center-based CR facility. Patients are automatically in contact with the care team involved in their care (medical directors, case managers, dietitians, exercise physiologists, etc.).

*The platform home page has been designed to enhance the user experience. Any resource from any module can be pushed directly to the homepage by the staff to avoid excessive navigation within the platform. It can be used to view information messages, to access specific tasks, and to setup reminders to perform certain tasks. The home page is scalable in time. It also evolves with patient progress within his/her program. The goal is to provide personalized care by displaying the right information at the right time to the right patient.*

*All modules (e.g., services) are independent from each other and can be activated or deactivated on request. All encompass sub-modules allowing for individualized patient progress through the program. The content of the sub-modules is fully customizable so it can be easily and effectively modified based on patient needs (e.g., removing diabetes information for non-diabetics or including smoking cessation information for current smokers, etc.) and remain in-line with center-based CR program content offerings.*

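### Section 3.9 judges whether an adverse event is study-related from EPIC emergency-room documents alone, so events that leave no such document may not be assessable and related ones may go unreported

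*Combined protocol and SAP*

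**What the plan says.** Section 3.9 (Adverse Events) sets out a short chain. First, "any AE notification will be notified to study PI". The investigator then judges relation to the study: "Which will deem its study relation by reviewing all EPIC ER documentations". Reporting follows from that judgement: "Any AE will be reported to IRB and recorded in intelliTrial if the PI deems study related". An event judged unrelated becomes a note in the subject's folder and does not enter intelliTrial. No other source for the judgement is named in the readable text, and there is no third category.

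Other sections describe where events may surface:

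- Section 3.5, on the mHealth platform: if an event or symptoms arise, "patients will be instructed to go to their local emergency room and/or call 911 for assistance". It adds that "The process for seeking medical attention is the same for all patients outside the center-based CR facility".
- Section 3.4 also recruits from "our subcontract site University of Minnesota Medical Center", whose "health network has 10 cardiac rehabilitation locations which provide cardiac rehabilitation services to ~4,000 new patients annually". Section 3.8 describes this help as being called on when needed.
- Section 3.3, on the comparators: CON and CON+ receive supervised exercise at the center. HOM+ participants are urged to exercise three times weekly and "will have a remote visit (either video or telephone visit) with Cardiac Rehab staff once a week for 12 weeks".
- Section 3.7: readmissions and deaths are gathered by study staff from follow-up visits and electronic health records.

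**The concern.** The relatedness decision controls reporting, so the evidence behind it should cover the ways in which events can reach the study. Emergency-room documents in one record system may not. A patient who follows the section 3.5 instruction may be treated at a hospital outside that system. A patient of the second network may have records elsewhere. A fall, or a faint that resolves during exercise, may need no emergency visit. A direct admission or a death at home may produce no emergency-room note.

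For an exercise trial, much of the relatedness question is whether the event happened during or shortly after exercise, and whether anyone was supervising. That is likeliest to be found in session records, weekly-visit notes and platform messages, none of which section 3.9 names. At stake is whether study-related events are recognized and reported. This matters more because section 3.7 plans a non-inferiority test of HOM+, the arm that exercises without center supervision, against CON.

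**Working it through.** The plan gives no adverse-event rate or capture rate, so there is no stated figure to reproduce. The check compares the evidence named in section 3.9 with the routes described elsewhere.

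| Route of the event | Emergency-room document in EPIC? | Other source in the protocol | Named in 3.9 for relatedness? |
|---|---|---|---|
| Visit to a local emergency room or a 911 call (3.5) | Not stated | Follow-up visits (3.5) | No |
| Patient of the second network (3.4) | Not stated | Follow-up visits (3.5) | No |
| Event in a center session, no emergency visit (CON, CON+) | None | Staff present at the session (3.3) | No |
| Event in home exercise, no emergency visit (HOM+) | None | Weekly remote visit, platform messages (3.3, 3.5) | No |
| Direct admission or death at home | Possibly none | Endpoint collection (3.7) | No |

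Three observations follow.

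1. In no row does section 3.9 name the source most likely to hold the facts. In two rows the named document cannot exist, because there was no emergency visit.
2. Section 3.7 already uses wider sources for readmission and death. That helps find those events, but nothing links it to the relatedness decision, and it does not cover events that were treated and released or never reached a hospital.
3. Section 3.9 offers two outcomes, related or not. It does not say what happens when the document is missing.

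For a possible difference by arm, let *c* be the share of events that is captured and attributed in an arm. Then:

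observed HOM+/CON ratio = true ratio × (*c* in HOM+ ÷ *c* in CON)

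As an illustration only, take a true ratio of 1 and *c* = 0.90 in CON. These values, and those for HOM+ below, are assumptions and do not come from the documents.

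| *c* in HOM+ | Calculation | Observed ratio |
|---|---|---|
| 0.60 | 0.60 ÷ 0.90 | 0.67 |
| 0.75 | 0.75 ÷ 0.90 | 0.83 |
| 0.90 | 0.90 ÷ 0.90 | 1.00 |
| 1.00 | 1.00 ÷ 0.90 | 1.11 |

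Equal capture leaves the ratio unchanged, although both counts fall. The ratio moves only if capture differs, and it can move either way. The documents do not fix *c* in any arm.

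**The case against.** The case on the other side is substantial, and it limits what can be claimed.

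- **Access to outside records is unstated, not excluded.** The investigator may be able to see or request them. This stands: the events may not be assessable, which is weaker than saying that they cannot be.
- **Notification is not confined to emergency visits.** Any notified event goes to the investigator, and no rule says that a missing document means unrelated. This stands too. Even so, the only evidence named for the decision remains the emergency-room document.
- **Text is redacted directly after section 3.9.** Further adverse-event provisions may be there, and their absence is not held against the plan. The point rests on the sentence that can be read.

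A reader might infer that home exercise will look safer than it is. The documents do not support that. The route to medical care is the same in every arm outside the center, and allocation is 1:1:1, so outside hospitals and the second network do not by themselves favor an arm. Staff may witness an event in a center session, but if no emergency visit follows it also leaves no emergency-room document. HOM+ has platform messaging and weekly contact, while CON lacks the platform. The readable text plans no comparison of adverse events between arms.

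A reader might also set 36 prescribed sessions against 12 remote visits as a measure of detection. It is not one: sessions prescribed are not sessions attended, attendance is itself an Aim 1 outcome, and both schedules span the same 12 weeks. Nor is follow-up after month 3 blind, since the 1-year visit and the section 3.7 endpoint collection cover it.

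**Conclusion.** The point holds as a gap in how relatedness is judged. Section 3.9 ties a decision that controls reporting to one kind of document, while the protocol's own instructions and recruitment plan allow events that may leave no such document. Some events may therefore not be assessable from the named source, and related events may go unreported.

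The size cannot be estimated. The documents give no event rate, no proportion of care received elsewhere and no number of patients from the second network. A difference by arm is plausible only for events around exercise, witnessed in center sessions and self-reported in HOM+, and its size and direction are uncertain. The conclusion assumes that the redacted lines do not already widen the sources. It calls for an inexpensive improvement to the safety procedures and does not touch the efficacy analyses.

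**What to change.** In section 3.9, replace review of EPIC emergency-room documents with review of all available sources:

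- CR session records, HOM+ weekly-visit notes and platform messages;
- the 3-month and 1-year visits;
- the health records already used for readmission and mortality in section 3.7;
- emergency or inpatient records from outside hospitals and the second network, where obtainable.

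For each event, record whether it occurred during or soon after exercise, with the time window defined in advance by the sponsor, and whether that exercise was supervised. Ask the same adverse-event question in all three arms at the existing 3-month and 1-year visits. These answers should add to the other sources and not replace them, because patients who die or miss a visit would otherwise be lost. Record an event with no obtainable documentation as *relation not assessable* rather than unrelated, and state what reporting follows from that category.

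The cost is protocol wording, one question at two visits that already take place, requests for outside records, slightly more review work and a few more events recorded or reported. Treatment, sample size and visit schedule do not change.
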